1.1. Study Objectives

The primary objectives of this study are as follows:

- The primary objective of the pharmacokinetics (PK) Lead-in Phase of this study is to evaluate the steady state PK and confirm the dose of sofosbuvir (SOF) in hepatitis C virus (HCV)-infected pediatric subjects.
- The primary objective of the Treatment Phase of this study is to evaluate the safety and tolerability of SOF + ribavirin (RBV) for 12 or 24 weeks in HCV-infected pediatric subjects with genotype 2 or 3, respectively

The secondary objectives of this study are as follows:

- The secondary objective of the PK Lead-in Phase of this study is to evaluate the safety and tolerability of 7 days of dosing of SOF + RBV in HCV-infected pediatric subjects.
- The secondary objectives of the Treatment Phase of this study are:
 - To determine the antiviral efficacy of SOF + RBV treatment in genotypes 2 and 3 HCV-infected subjects separately, as assessed by the proportion of subjects with sustained viral response 12 weeks after discontinuation of therapy (SVR12)
 - To determine the antiviral efficacy of SOF + RBV treatment in genotypes 2 and 3 HCV-infected subjects separately, as assessed by the proportion of subjects with sustained viral response 4 and 24 weeks after discontinuation of therapy (SVR4 and SVR24)
 - To evaluate the kinetics of circulating HCV RNA during treatment and after treatment discontinuation
 - To evaluate the emergence of viral resistance to SOF during treatment and after treatment discontinuation
 - To evaluate the palatability of SOF oral granules at Day 1, as applicable
 - To evaluate the effect of growth and development on pediatric subjects during and after treatment

The exploratory study objective is as follows:

- PPD

1.2. Study Design

This is an open-label, multi-cohort, two-part study evaluating the PK, safety, and efficacy of SOF + RBV in chronic HCV-infected pediatric subjects.

The study will enroll both treatment-naïve and treatment-experienced pediatric subjects, with up to 20 subjects allowed to be treatment experienced. Approximately 100 total subjects will be enrolled as follows:

- Approximately 50 adolescents aged 12 to < 18 years
- Approximately 50 children aged 3 to < 12 years

Subjects of 3 age groups will be enrolled in a sequential fashion: 12 to <18 years old, followed by 6 to <12 years old, and 3 to <6 years old.

Eligible subjects will receive the following regimen based on HCV genotypes:

- Genotype 2 subjects: SOF + RBV for 12 weeks
- Genotype 3 subjects: SOF + RBV for 24 weeks

Therefore, subjects are grouped into the treatment groups specified in [Table 3-1](#) according to their age groups and HCV genotypes.

The schedules of assessments for the study are provided as appendixes to the SAP (see Study Procedures Table, [Appendix 1](#)).

1.2.1. PK Lead-in Phase

The PK Lead-in Phase will evaluate and/or confirm the age appropriate SOF dose by analyzing PK, safety, and antiviral activity of SOF + RBV through 7 days of dosing for each cohort.

Up to 10 genotype 2 or 3, treatment-naïve pediatric eligible subjects will be sequentially enrolled into each of the following 3 cohorts:

- Cohort 1: 12 to < 18 years old, weighing \geq 45kg
- Cohort 2: 6 to < 12 years old, weighing \geq 17kg and \leq 45kg
- Cohort 3: 3 to < 6 years old

The study will start with Cohort 1 where subjects will receive SOF (400 mg adult tablet or 4×100 mg tablets if determined necessary based on SOF swallowability assessment) + RBV for 7 days with intensive PK conducted on Day 7.

Cohort 2 subjects will receive 200 mg SOF (2×100 mg tablets or 4×50 mg capsules if determined necessary based on the SOF swallowability assessment) + RBV for 7 days with intensive PK conducted on Day 7.

Cohort 3 subjects weighing ≥ 17 kg will receive 200 mg SOF (4×50 mg capsules containing granules) + RBV for 7 days with intensive PK conducted on Day 7. Cohort 3 subjects weighing < 17 kg will receive 150 mg SOF (3×50 mg capsules containing granules) + RBV for 7 days with intensive PK conducted on Day 7.

Subjects enrolled in the PK Lead-in Phase will immediately enroll in the Treatment Phase as they completed Day 7 of the PK Lead-in Phase. Subjects continue dosing with SOF + RBV with no interruption of study drug administration.

1.2.2. Treatment Phase

Additional genotypes 2 and 3 HCV-infected children will be enrolled into the Treatment Phase upon confirmation of the appropriateness of the dose from the PK Lead-in Phase. The Treatment Phase will be initiated sequentially by age cohort as defined in Cohorts 1, 2, and 3 of the PK Lead-in Phase.

Subjects who participated in the PK Lead-in Phase will immediately roll over into the Treatment Phase with no interruption of study drug administration until the appropriateness of the dose has been confirmed by PK and safety results from the PK Lead-in Phase. The first visit in the Treatment Phase for these subjects will be the Week 2 visit.

1.2.3. Study Duration

The total time to complete all study visits is up to approximately 40 weeks for subjects treated with 12 weeks of therapy and 52 weeks for subjects treated for 24 weeks of therapy including the following periods:

- 28-day (4-week) screening period
- 12 or 24 week treatment period
- 24-week post-treatment period

1.3. Sample Size and Power

With approximately 50 subjects enrolled into 12 to < 18 years of age group and approximately 50 subjects enrolled into 3 to < 12 years of age group of the Treatment Phase, a 2-sided 95% confidence interval of the SVR12 rate will extend at most 11.1% in both directions from the observed SVR12 rate, assuming the expected SVR12 rate is 80%. In addition, a sample size of 100 subjects will provide over 80% power to detect an 11% improvement in SVR12 rate from 80% to 91% using 2-sided one-sample binomial test at significance level of 0.05.

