**Statistical Methods:**

For the PK Lead-in, plasma PK parameters  $C_{max}$ ,  $T_{max}$ ,  $C_{last}$ ,  $T_{last}$ ,  $C_{tau}$ ,  $AUC_{tau}$ , and  $t_{1/2}$  will be estimated. The PK parameters will be summarized by cohort. The effect of age and SOF dose on PK (SOF and GS-331007) will be explored.

For the Treatment Phase, the primary safety endpoint is any AE leading to permanent discontinuation of study drug and will be summarized by age group, by GT and overall. The key efficacy endpoint is SVR12 in all enrolled and treated subjects and will be summarized by age group, by genotype, by overall and by age group and GT. Point estimate and its 95% confidence interval will be provided.

In addition, SVR12 will be compared with historical SVR12 rate of 80% from pegylated interferon + ribavirin for pediatric GT-2 and GT-3 subjects {20280}, using two-sided exact one-sample binomial test at the 0.05 significance level.

Secondary efficacy endpoints are SVR4, SVR24, breakthrough and relapse.

Palatability of SOF oral granules will be summarized using descriptive statistics by appropriate age group, by genotype, by overall and by age group and genotype.

Subgroup analysis on SVR12 will be performed by treatment experience (treatment-naive vs. experienced) and GT. Other clinically relevant subgroup analyses may be conducted as appropriate (i.e., assuming that adequate numbers of subjects in these subsets are available for analysis).

All continuous endpoints will be summarized using an 8-number summary (n, mean, standard deviation, median, Q1, Q3, minimum, maximum). All categorical endpoints will be summarized by number and percentage of subjects who meet the endpoint definition.

Safety endpoints will be analyzed by the number and percent of subjects with events or abnormalities for categorical values or 8-number summary (n, mean, standard deviation, median, Q1, Q3, minimum, maximum) for continuous data by age group, by GT, by overall and by age group and GT.

With approximately 50 subjects enrolled into each age group of Treatment Phase, a two-sided 95.0% confidence interval of the SVR12 rate will extend at most 11.1% in both directions from the observed SVR12 rate, assuming the expected SVR12 rate is 80%. In addition, a sample size of 100 subjects will provide over 80% power to detect an 11% improvement in SVR12 rate from 80% to 91% using two-sided one-sample binomial test at significance level of 0.05.

---

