#### **9.6.1. Primary Efficacy Analysis**

The key efficacy endpoint is SVR12 (HCV RNA < LLOQ 12 weeks after completion of treatment) in the FAS population. Point estimate and its 95% confidence interval will be provided.

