### **9.9. Sample Size**

With approximately 50 subjects enrolled into each age group of Treatment Phase, a two-sided 95.0% confidence interval of the SVR12 rate will extend at most 11.1% in both directions from the observed SVR12 rate, assuming the expected SVR12 rate is 80%. In addition, a sample size of 100 subjects will provide over 80% power to detect an 11% improvement in SVR12 rate from 80% to 91% using two-sided one-sample binomial test at significance level of 0.05.

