6.1.3. Analysis Methods for the Key Efficacy Endpoint

A sequential test method was used to firstly perform the above statistical test in the adolescent subjects (ie, 12 to < 18 years of age). The SVR12 rate for adolescents was compared with the historical SVR12 rate of 80% using a 2-sided exact 1-sample binomial test at the 0.05 significance level. The test in adolescents was described in a separate SAP for Adolescents SVR12 Analysis. Only if the superiority is demonstrated in adolescents, the SVR12 rate in the remaining subjects (ie, children aged 3 to < 12 years) will be compared with 80% at the 0.05 significance level.

The point estimates of SVR12 rate and 2-sided 95% exact CI based on Clopper-Pearson method will be provided for the SVR12 rate by treatment group and total in each age group {Clopper 1934}.

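### The stated SVR12 precision of 11.1 points in both directions is a Wald half-width; the planned Clopper-Pearson interval at 40/50 reaches 13.7 points down and 10.0 up

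*SAP*

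**What the plan says.** SAP section 1.3 sets the scene with two groups of about 50 each: adolescents (12 to under 18) and younger children (3 to under 12). For these it states that "a 2-sided 95% confidence interval of the SVR12 rate will extend at most 11.1% in both directions from the observed SVR12 rate", on an expected SVR12 rate of 80%. Protocol section 9.9 carries the same claim ("a two-sided 95.0% confidence interval of the SVR12 rate will extend at most 11.1% in both directions from the observed SVR12 rate"), and so does the Statistical Methods part of the synopsis. None of the three places names the interval method behind the figure.

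The analysis sections differ in how specific they are. Protocol section 9.6.1 says only: "Point estimate and its 95% confidence interval will be provided". SAP section 6.1.3 is explicit: "2-sided 95% exact CI based on Clopper-Pearson method will be provided for the SVR12 rate by treatment group and total in each age group". The total in each age group is the group of about 50 to which the precision statement refers.

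**The concern.** The sample-size section describes one interval and the analysis section plans another. A bound that is equal on both sides of the observed rate is a property of the Wald interval. Clopper-Pearson intervals at high response rates are asymmetric, with the longer arm pointing downwards. If 11.1 came from the Wald formula, the lower limit the study reports would lie further from the estimate than the plan promises.

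This is the only precision statement for each age group. The lower side also matters most here, because the hypothesis in SAP 6.1.2 compares SVR12 with a historical 80%. A reader relying on 11.1 points would expect a lower limit near 69% at an observed 80%. The planned method gives about 66%.

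**Working it through.** **Inputs.** Two-sided 95% confidence, n = 50 per age group and an expected rate of 80%, so 40/50 (SAP 1.3, protocol 9.9). Reporting method: Clopper-Pearson (SAP 6.1.3). Null rate 80% (SAP 6.1.2). Alternative for power 91% (SAP 1.3).

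**Reproducing the plan's figure.** The Wald half-width is z × √(p(1 − p)/n) = 1.96 × √(0.8 × 0.2/50) = 0.1109, or 11.1 points. Alternatives at 40/50:

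- Continuity-corrected Wald: 12.1 points each way.
- Wilson: 13.0 down, 8.8 up.
- Agresti-Coull: half-width 11.1, but centred on 77.9%, not on the observed 80%.
- Clopper-Pearson: 13.7 down, 10.0 up.

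Of these, only uncorrected Wald gives 11.1 symmetrically about the observed rate.

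**The planned interval.** Lower limit = Beta quantile 0.025 with parameters (x, n − x + 1). Upper limit = Beta quantile 0.975 with parameters (x + 1, n − x). At x = 40, n = 50 these are 66.28% and 89.97%. The arms are 80 − 66.28 = 13.72 below and 89.97 − 80 = 9.97 above. The lower arm exceeds the stated maximum by 13.7 − 11.1 = 2.6 points; the upper arm is within it.

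**Other results at n = 50:**

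| Observed | Clopper-Pearson 95% CI | Points below | Points above | Wald half-width |
|---|---|---|---|---|
| 39/50 | 64.0% to 88.5% | 14.0 | 10.5 | 11.5 |
| 40/50 | 66.3% to 90.0% | 13.7 | 10.0 | 11.1 |
| 45/50 | 78.2% to 96.7% | 11.8 | 6.7 | 8.3 |
| 46/50 | 80.8% to 97.8% | 11.2 | 5.8 | 7.5 |
| 47/50 | 83.5% to 98.7% | 10.5 | 4.7 | 6.6 |

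Over all x from 0 to 50, the lower arm is 11.1 points or less only for x = 0 to 12 and x = 47 to 50. For any result this trial could plausibly give, that means 47/50 or better.

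**Averaged over sampling.** Weighting the lower arm by Binomial(50, 0.80) gives a mean of 13.6 points, about 2.5 beyond the stated figure. Weighting by Binomial(50, 0.91) gives 11.3, about 0.2 beyond.

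**Effect on the test.** The two-sided exact test against 80% gives p = 0.079 at 45/50 and p = 0.033 at 46/50. The Clopper-Pearson lower limit first exceeds 80% at 46/50 as well (80.8%). There the lower arm is 11.2, only 0.1 point beyond the stated figure.

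**Scale.** At an observed 80%, the lower arm is 11.3 points with 56/70 and 10.8 with 60/75. The word approximately before 50 does not absorb the gap: 44/55 still gives 13.0.

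**The case against.** The calculation is not wrong in itself. 11.09 is the correct Wald half-width, normal-approximation precision is common in sample-size paragraphs, and nothing later in the plan uses the number. SVR12 supports a secondary objective, the exact intervals will be reported whatever section 1.3 says, and SAP 6.1.3 describes the adolescent comparison as already made. All of this stands, and it keeps the point small. It does not reconcile the two SAP sections: section 1.3 neither names Wald nor calls the figure approximate, and it presents it as a maximum.

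The 80% case with its lower arm is also the least favourable way to show the gap. The average half-width at 40/50 is (13.7 + 10.0)/2 = 11.8, only 0.7 above 11.1, and at a true rate of 91% the lower arm is close to the stated figure. That is fair, but 80% is the rate the plan itself assumes, and its claim covers both directions.

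The Wald half-width of 11.5 at 39/50 can be answered by reading the claim as limited to rates of 80% or more. There Wald is widest at 80%, so the maximum is coherent. On that reading the 39/50 result is a weakness of wording, not a second error. The main point does not depend on it.

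Finally, the protocol names no interval method, so it does not contradict itself. The direct conflict is within the SAP, and the protocol only repeats the figure.

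**Conclusion.** The concern holds. The 11.1 points are a Wald half-width at n = 50 and 80%, and the Clopper-Pearson interval the SAP plans for the same groups does not deliver them. At 40/50 the lower arm is 13.7 points, 2.6 beyond the stated maximum; the upper arm of 10.0 is inside it. This is a mismatch between the precision statement and the analysis method, not a miscalculation.

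The size rests on exactly 50 subjects per age group and the plan's own 80%; the excess shrinks to about 0.2 point on average if the true rate is 91%. Intervals by genotype within an age group will rest on fewer subjects and be wider still, by an amount the documents do not allow one to state. No test decision, planned sample size or stated power at 100 subjects changes. The sentence should be corrected because it is wrong as written and cheap to put right.

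**What to change.** In SAP section 1.3, replace the precision sentence with one to this effect: with 50 subjects in an age group and an observed SVR12 of 80% (40/50), the two-sided 95% Clopper-Pearson interval is 66.3% to 90.0%, that is 13.7 points below and 10.0 points above the observed rate. Remove the wording that presents the figure as a maximum. Make the same change in protocol section 9.9 and the synopsis at the next amendment; it does not warrant an amendment of its own.

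A lighter alternative is to keep 11.1 and label it a normal approximation at 80%, but that still leaves the reader without the precision of the interval that will be reported.

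The cost is one sentence in three places and a slightly less favourable stated precision. No change to the sample size is proposed.

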6.1.2. Statistical Hypothesis for the Key Efficacy Endpoint

The null (H₀) and alternative (H₁) hypotheses used to assess the superiority of SOF + RBV relative to the historical SVR12 rate of 80% are as follows:

H₀: SVR12 rate = 80%

H₁: SVR12 rate ≠ 80%

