6.4. Changes From Protocol-Specified Efficacy Analyses

Instead of comparing the SVR12 rate in all treated subjects (3 to < 18 years of age) against the historical SVR12 rate of 80% by using the 2-sided exact 1-sample binomial test at the 0.05 significance level as specified in the protocol, a sequential test method was used to firstly perform the above statistical test in the adolescent subjects (12 to < 18 years of age). Only if the superiority is demonstrated in adolescents, the SVR12 rate in the remaining subjects (3 to < 12 years of age) will be compared with 80% at the 0.05 significance level. The test in adolescents was described in a separate SAP for Adolescents SVR12 Analysis. Details of the test in this Final Analysis are described in Section [6.1.3](#).

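### SAP 1.3 still claims over 80% power from a pooled test of 100 subjects, but the SAP now runs two sequential tests of about 50 each, with about 53% power for the first and 28% for both at the planned 91% rate

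*SAP*

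**What the plan says.** SAP 1.3, repeating Protocol 9.9, makes two sizing statements. One is about precision: with about 50 subjects per age group, the 95% confidence interval for SVR12 extends at most 11.1 percentage points either way at a rate of 80%. The other is about power: "a sample size of 100 subjects will provide over 80% power to detect an 11% improvement in SVR12 rate from 80% to 91"%. It assumes a two-sided binomial test at the 5% level.

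Protocol 9.6.2 supplies the test behind the power statement, an exact binomial comparison of SVR12 with 80%. SAP 6.4 describes this as a comparison in all treated subjects and replaces it: "Instead of comparing the SVR12 rate in all treated subjects (3 to < 18 years of age) against the historical SVR12 rate of 80"%, a sequence is used. Under SAP 6.1.3 the adolescents are tested first, "using a 2-sided exact 1-sample binomial test at the 0.05 significance level". Then: "Only if the superiority is demonstrated in adolescents, the SVR12 rate in the remaining subjects" is compared with 80%, again at 0.05.

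SAP 1.2 gives the group sizes: "Approximately 50 adolescents aged 12 to < 18 years" and "Approximately 50 children aged 3 to < 12 years". Neither SAP 1.3 nor SAP 6.4 gives the power of the sequential tests.

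**The concern.** The only power figure in the SAP describes an analysis that the same document has given up. Halving the sample for each test lowers its power, and the gate lowers the chance of a claim in children further, because they are formally tested only if the adolescents pass.

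The comparison with 80% is the only efficacy hypothesis stated in the SAP (section 6.1.2). Under the plan's own alternative, the first test has close to an even chance of success, and a formal claim in children has about a one-in-four chance at the design stage. For example, 45 of 50 adolescents responding (90%) would fail the gate, and the children would not be tested. A reader relying on SAP 1.3 could take that as a miss in a study with over 80% power.

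**Working it through.** **Inputs.** The null rate is 0.80 (SAP 6.1.2: "relative to the historical SVR12 rate of 80"%). The alternative is 0.91 and alpha is 0.05 two-sided (SAP 1.3). The test is exact binomial (SAP 6.1.3), with about 50 per group (SAP 1.2). No allowance for dropout is needed: SAP 3.5.1 counts an unbracketed missing SVR12 as failure, so n is not reduced.

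**Method.** Find the smallest r with P(X ≥ r | n, 0.80) ≤ 0.025. Power is then P(X ≥ r | n, 0.91). The check was repeated with the other common two-sided exact test, which orders outcomes by their probability under the null (the small-p method).

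**The plan's own figures, pooled n = 100.**
- P(X ≥ 88 | 100, 0.80) = 0.0253, just too large. P(X ≥ 89) = 0.0126, so r = 89.
- Power = P(X ≥ 89 | 100, 0.91) = 81.2%.
- The small-p method rejects from 88 (p = 0.045), with power 88.6%. The normal approximation gives 86.5%.
- All three exceed 80%, so the statement is correct for the pooled test.
- The half-width 1.96 × √(0.80 × 0.20 / 50) = 0.111 also reproduces.

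**The tests now planned, n = 50 each.**
- P(X ≥ 45 | 50, 0.80) = 0.0480, too large. P(X ≥ 46) = 0.0185, so r = 46.
- The small-p method has the same cut-off (p = 0.033 at 46, 0.079 at 45).
- Power = P(X ≥ 46 | 50, 0.91) = 0.5277, or 52.8%. The normal approximation gives 49.1%.
- The two groups contain different subjects, so the probability that both tests succeed is 0.5277 × 0.5277 = 0.2784, or 27.8%. Because of the gate, this is also the design-stage power for the children's claim.

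**Allowing for approximate group sizes.** Exact power is saw-toothed in n. At a true rate of 91%, equal-tailed test, same n in both groups:

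| n per group | Reject at | Power, one test | Both tests |
|---|---|---|---|
| 45 | 42 | 41.4% | 17.2% |
| 47 | 44 | 37.9% | 14.4% |
| 48 | 44 | 56.4% | 31.8% |
| 50 | 46 | 52.8% | 27.8% |
| 52 | 48 | 49.2% | 24.2% |
| 54 | 50 | 45.8% | 21.0% |
| 55 | 50 | 62.5% | 39.1% |

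The lowest and highest values for n from 45 to 55 are those at 47 and 55. At n = 47 the small-p method rejects from 43, with power 58.2%. Power at 91% stays at or above 80% only from about n = 94 per test.

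**Allowing for the true rate, n = 50 per group.**

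| True SVR12 | One test | Both tests |
|---|---|---|
| 91% | 52.8% | 27.8% |
| 93% | 72.9% | 53.2% |
| 94% | 82.1% | 67.3% |
| 95% | 89.6% | 80.3% |

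So 80% power needs a true rate of about 94% for one test and about 95% for both.

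**The case against.** The strongest reply is that the sentence is true as written. It names its own sample size, reproduces exactly, and carries over the protocol's justification for enrolling 100. SAP 6.4 declares the change of test openly. On this view the defect is a statement left unrevised, not a miscalculation. That description is fair, but the result is still that the SAP's only power figure does not apply to any test it plans.

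Second, the SAP describes the adolescent test in the past tense and refers to a separate SAP, which is not among the documents and may state its own power. If that test has already succeeded, the relevant figure for the children is 52.8%; 27.8% holds only at the design stage. This stands as a qualification. Both figures are well below 80%, and a statement elsewhere would not correct SAP 1.3, which also covers the children's test.

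Third, the consequences are bounded. The primary endpoint of the Treatment Phase is discontinuation because of adverse events (Protocol 9.1.2), and the protocol places the comparison with 80% under secondary efficacy analysis. Confidence intervals are reported whatever the gate shows, the 11.1-point precision statement remains correct for the age groups, and testing in a fixed order at 0.05 controls the type I error. Misreading of a failed gate is a risk, not a certainty. All of this stands and limits the stakes, but none of it makes the power statement right.

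Finally, the point values 53% and 28% look more precise than group sizes of about 50 allow, and power rises steeply with the true rate. That is a good reason to quote ranges. The rate the plan assumes is nevertheless 91%.

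**Conclusion.** The concern holds. The power stated in SAP 1.3 is that of a pooled test which SAP 6.1.3 and 6.4 have replaced. For the tests now planned, exact power at 91% is 52.8% for the adolescents and 27.8% for the full sequence, against a stated figure of over 80%. These values assume exactly 50 subjects in each group, a true rate of 91% in both, and independence between groups. For 45 to 55 per group the equal-tailed ranges are 37.9% to 62.5% and 14.4% to 39.1%, so no reasonable reading of the planned sizes restores 80%. Power would be adequate if the true rate were about 95%, but the SAP does not assume that. Type I error is not in question.

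**What to change.** - **SAP 1.3:** remove the 100-subject power sentence, or keep it clearly labelled as the basis of the protocol's original pooled design. Add the power of the two planned tests at 91%: about 53% for each test on its own and about 28% for the sequence at the design stage, with the ranges for 45 to 55 per group. Add the figures at a true rate of 95% (about 90% each, 80% for both), so that the dependence on the assumption is visible.
- **SAP 6.4:** state the loss of power as a consequence of replacing the pooled test, and cross-refer to the separate adolescent SAP for any power statement made there.
- **Optional:** report the protocol's pooled comparison as well, marked as descriptive and outside the testing sequence, so that it does not become a second route to a claim.

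The cost is SAP wording and a less favourable stated power. No extra subjects are needed, and enrolment, data collection and the testing sequence do not change.
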